Figure 1. Proof of principle demonstration of differences in peripheral retinal thickness measurements using OCT. The OCT beam is shown in red pivoting through the iris. The eye model is based on published schematic eyes [52,58]. The desired thickness is the surface normal thickness h . The OCT measured thickness is along the A scan in red. The difference between h and the OCT measured thickness increases as the half scan angle β increases.

offered for this measurement problem, and the net result clinically is that cataract surgery planning for this population is confusing and outcomes are unpredictable [23]. This unpredictability is difficult in a clinical environment where patients routinely expect 20/20 spectacle free vision after refractive and cataract surgeries.

In the back of the eye, measuring surface geometry is also diagnostically important (please see supporting letter from Collaborator [name].). The standard simple axial length measure has proven inadequate for understanding the myopic (near-sighted) eye and its development. Specific three-dimensional alterations in the shape of the posterior eye in those with myopia have been correlated with progression of this disease [24] and with vision threatening pathology [25,26]; hence, posterior eye shape could be used for risk-stratification with appropriate follow-up and counselling. Recently, off-axis peripheral treatment of refractive error (not standard axial refractive correction) has demonstrated promising arrest of myopia development [27]. Though it would be reasonable to measure posterior eye shape with long available ophthalmic ultrasound, a search of the literature (PubMed using “eye” AND “shape” AND “myopia” AND “ultrasound”) returned only one paper using ultrasound for this purpose [28]; the remainder used ultrasound only to measure axial length. Instead, posterior eye shape is currently obtained using MRI [24-26,29-31] with its attendant cost and logistical barriers. Lowering the cost and logistical barriers to obtaining the shape of the posterior eye using ubiquitous, non-contact OCT would allow more widespread clinical use of this measurement for risk stratification of myopes and for study of myopia progression. Further, using OCT provides a 10-fold increase in resolution over posterior segment ophthalmic ultrasound for measurement accuracy and also provides the layered microanatomy that is used widely by clinicians and researchers.

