The spatial inaccuracy of current posterior eye OCT images results from the current standard practice of simply displaying A-scans next to each other in a parallel fashion. This fails to account for the actual, non-parallel transit of OCT light through the eye. The objective of this aim is two-fold. The *first objective* is to develop and validate algorithms for accurately portraying the posterior eye in OCT images by ray tracing the OCT imaging paths through the imaged anterior eye. The *second objective* is to then test the hypothesis that corrected posterior eye OCT images will be comparable to MRI of the same eyes.

The *rationale* for this aim is that successful completion of this aim will produce posterior eye OCT images faithful enough to replace MRI imaging for studying posterior eye shape biomarkers. Our expectation is that this development will remove cost and logistical barriers limiting more widespread study of posterior eye shape as a diagnostic biomarker for myopia progression, particularly in children and young adults.

SA3. Justification & Feasibility. In an initial study by the P.I. [4], we enrolled subjects in an IRB approved study who had recently obtained head MRIs for their medical care but did not have ocular disease. We performed ocular biometry and retinal

[figure not shown]

FIGURE 9. Representative original and spatially (numerically) corrected retinal OCT B scans (top R) and comparison to MRI (bottom L and R) [4]. The posterior eye appears flat in the original image (top L) and has a more plausible physiologic curvature after spatial correction (top R). Reported values in the literature for posterior eye curvature (R_c) range from 10.8-14.1 mm [34]. Spatial correction in the 10 eyes in this study significantly reduced the difference between OCT and MRI posterior eye shape (bottom L). In this small preliminary study, there remains a bias and a possible trend between the OCT measures and MRI (bottom R).

SDOCT on these subjects. Using commercial ray tracing software, we modeled the commercial SDOCT system and the subjects' eyes using their measured biometric data. The spatial orientation of the OCT scan paths was then used to reorient each OCT A-scan to its modeled location in MATLAB. Using this correction, there was a significant reduction in differences and variability between posterior eye shape measured by OCT and MRI (Fig. 9).

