Despite the overall improvement in posterior eye OCT shape in this pilot study, there remained a bias between the OCT measures and MRI. The possible sources of error in this preliminary work (other than small

sample size) include the lower resolution of these non-orbital MRI scans, the use of schematic model anterior eyes, motion errors, and the unknown system-to-cornea distance to control for scan magnification.

In this proposal, we will perform a prospective study with dedicated orbital MRIs, with measured and model-free determination of all ocular surfaces, with decreased patient motion from the faster SSOCT system, and with direct measurement of the system-to-cornea distance (see SA1.Research Design.System Calibration). With these improvements, we anticipate that we will decrease the curvature difference between MRI and OCT to less than a millimeter (resolution of our MRI). Further, we will compare surface topographies of myopic patients with known morphometric changes (e.g. staphylomas) imaged with MRI and OCT.

SA3. Research Design. Algorithm development and validation. We will extend our previously developed three-dimensional refraction correction algorithms [20] to perform ray tracing of the OCT scan paths through the ocular surfaces contained within the whole eye OCT images. The anterior eye image content will be segmented and corrected of optical distortions as in Aim 2 (refraction, non-telecentricity, motion). Group refractive indices for our light source ($\lambda_0 = 1060$ nm) will be used for refraction correction as described in detail in SA2.Research Design.Algorithm Development. For the lens, we will measure the group index for IOLs, and use a polynomial model for natural lenses [52] as was used in our pilot work [4]. The retinal layers of the posterior eye will also be segmented in preparation for post-processing [53]. With a known system topology, measured and hence known system-to-cornea distance per patient, and an accurate representation of the anterior eye components, we will determine the spatial orientation of the OCT scan paths to the posterior eye. With these OCT scan paths, the posterior eye A-scans will be properly repositioned spatially to restore anatomic accuracy.

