Each enrolled subject will undergo the following imaging: optical biometry (LenStar, Haag-Streit), whole eye OCT, and MRI imaging. MRI will be performed on the clinical research scanners at the Duke Brain Imaging and Analysis Center (see support letter from director [name]). Annually, with the assistance of dedicated research coordinators, they image over 2000 subjects with MRI for over 70 research projects. Their scanner (GE) has a magnetic field strength of 3.0 Tesla. A high resolution T1 FSPGR sequence will be used to acquire images of the subject's eyes. Images will be acquired in the axial plane, with FOV=25.6cm, TR=8ms, TE=3ms, flip angle=12, 512x512x50 imaging matrix, completely covering the eyes. A second T2 weighted sequence will be acquired at the same slice prescription with TR=3s and TE=25ms. With these scan parameters, each voxel will be 0.5 mm^3 . During scanning, a fixation target will be provided to minimize eye motion during acquisition.

[figure not shown]

FIGURE 10. General overview of clinical study design to determine the difference between OCT and MRI posterior eye images. Using radius of curvature as a general measure of shape, we will compare the paired differences between the two modalities. In a second study in subjects with staphylomas, we will use root mean square difference to describe the topographic differences between the two registered modalities.

The radius of curvature of the posterior eye will be measured via surface fitting of the posterior eye data from OCT and MRI. To have 80% power to detect a 0.5 mm difference in radius of curvature between OCT and MRI using a paired one-sample t-test, we will need to enroll a minimum of 48 normal pseudophakic subjects (PROC POWER, SAS v9.3). This power calculation assumes that with our whole eye OCT and improved algorithms, we will halve the standard deviation of the difference between MRI and OCT found in our initial study (2.3 mm), resulting in an estimated standard deviation of 1.2 mm. At a 0.5 mm difference, we will be at the effective voxel resolution of the MRI scans and should also have more than enough resolution to identify the large-scale topographic abnormalities noted in previous MRI studies of myopia [25,26].

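### Aim 3, Group 1: the 0.5 mm detectable mean difference over 48 subjects cannot support the claim of resolution to identify abnormalities, and no single-eye agreement result is planned

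*Combined protocol and SAP*

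**What the plan says.** The sample-size paragraph under SA3. Research Design, Group 1, opens "To have 80% power to detect a 0.5 mm difference in radius of curvature between OCT and MRI using a paired one-sample t-test" and arrives at a minimum of 48 normal pseudophakic subjects. The SD of the OCT–MRI difference in the initial study was 2.3 mm. The plan assumes that the new system and algorithms will halve it, "resulting in an estimated standard deviation of 1.2 mm".

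The next sentence takes the 0.5 mm, places it at the effective voxel resolution of the MRI, and concludes that the study "should also have more than enough resolution to identify the large-scale topographic abnormalities noted in previous MRI studies of myopia".

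Three other places bear on how this will be read:

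- SA3. Justification & Feasibility: "we anticipate that we will decrease the curvature difference between MRI and OCT to less than a millimeter", a figure described there as the MRI's resolution.
- Significance: "posterior eye shape could be used for risk-stratification with appropriate follow-up and counselling".
- SA3. Expected Outcomes: Aim 3 is to supply the basis for OCT taking over from MRI in ophthalmic studies of eye shape, and risk stratification is named again as a clinical use.

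For Group 1 the text and the Figure 10 caption describe one comparison, the paired difference in fitted radius. No limits of agreement and no acceptable per-eye difference are stated. For Group 2 (20 highly myopic patients) a root mean square deviation between registered surfaces is planned, without an acceptance threshold.

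**The concern.** Two different quantities are run together. The difference that a paired t-test can detect depends on the SD divided by the square root of the sample size, so it can be made as small as one likes by enrolling more subjects. Voxel resolution, and the ability to identify an abnormality, concern one image of one eye, and enrolment does not change them. For the fitted radius, the planned SD of the differences describes how closely the two methods agree in one eye.

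What is at stake is the conclusion that Group 1 can support. The stated goal for this group is that OCT should be spatially comparable to MRI in a normal eye, and risk stratification is done patient by patient. The study could meet all its planning assumptions, report a mean difference near zero, and be read as showing agreement in individual eyes that its data had not shown.

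**Working it through.** **Inputs.** Mean difference to detect 0.5 mm, power 80%, n = 48, planned SD 1.2 mm, pilot SD 2.3 mm: all from SA3. Research Design, Group 1. Half of 2.3 is 1.15, which the plan rounds up to 1.2. Alpha and sidedness are not stated for Aim 3; two-sided 0.05 is assumed, alpha being the value given for Aim 2. One difference per subject is assumed.

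**1. Reproduce the plan's sample size.** Exact noncentral-t power for a paired t-test, difference 0.5, SD 1.2, two-sided 0.05: the smallest n reaching 80% is 48, with power 80.7%. The normal approximation is close: (1.2 × (1.960 + 0.842) / 0.5)² = 45.2, so 46. A one-sided test would need only 38. The figure of 48 is therefore right for a two-sided test of the mean.

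**2. What the 0.5 mm describes.** Standard error of the mean difference = 1.2 / √48 = 0.173 mm. The 95% confidence interval has half-width 2.012 × 0.173 = 0.35 mm. Both shrink with n.

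**3. Agreement in a single eye.** 95% limits of agreement = bias ± 1.96 × SD, for normally distributed differences. These do not shrink with n.

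| SD | Bias | 95% limits |
|---|---|---|
| 1.2 mm (planned) | 0 | ±2.35 mm |
| 1.2 mm (planned) | 0.5 mm | −1.85 to +2.85 mm |
| 1.15 mm (unrounded half) | 0 | ±2.25 mm |
| 2.3 mm (pilot, not halved) | 0 | ±4.51 mm |

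The planned limit is 2.35 / 0.5 = 4.7 times the 0.5 mm figure.

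**4. Proportion of eyes disagreeing, at SD 1.2 mm and zero bias.**

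- By more than 0.5 mm: 2 × (1 − Φ(0.5/1.2)) = 67.7%.
- By more than 1 mm: 2 × (1 − Φ(1/1.2)) = 40.5%.

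For 95% of eyes to agree within 0.5 mm, the SD would have to be about 0.5 / 1.96 = 0.26 mm.

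**5. How well 48 subjects would estimate the limits.** Standard error of one limit = 1.2 × √(1/48 + 1.96²/(2 × 47)) = 1.2 × √(0.0208 + 0.0409) = 0.298 mm. A 95% interval for each limit is about ±1.96 × 0.298 = ±0.58 mm. The planned sample gives a usable estimate without enlargement.

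**The case against.** The strongest reply is that the disputed sentence concerns topography, whereas the 1.2 mm is the SD of a fitted global radius, which the Figure 10 caption calls only a general measure of shape. An error in radius is not an equal error in the surface. Take a sphere of 12.5 mm radius (the model-eye hemisphere) over the roughly 120° field about the eye's centre, assumed symmetric. With apices aligned, a radius error ΔR displaces the surface by about ΔR × (1 − cos θ). Area-weighted to θ = 60°, the root mean square is ΔR × 0.5/√3 = 0.289 × ΔR: about 0.35 mm for 1.2 mm and 0.68 mm for 2.35 mm. The difference also contains MRI error. This stands. A reader might infer that OCT would miss staphylomas. The documents do not support that: they give no size for the large-scale abnormalities, and topography has its own per-eye analysis in Group 2. But the reply does not rescue the sentence, which rests its claim on the 0.5 mm and not on a surface error.

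Three further points also stand.

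- The plan never says that 0.5 mm is a per-eye figure. That reading comes from the comparison with voxels and from the talk of identifying abnormalities.
- The anticipated takeover from MRI is framed around ophthalmic studies, some of which need only group means. Clinical risk stratification is a prospective benefit, not a Group 1 decision rule.
- Limits of agreement follow directly from the mean and SD of differences that the study will compute anyway, and Figures 9 and 10 could not be seen. The text nevertheless commits to no such result.

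One comparison is tempting but should not be pressed. The limits span 4.7 mm, while the Figure 9 caption says that literature values for posterior curvature "range from 10.8-14.1 mm", a width of 3.3 mm. The caption does not call these normal eyes, or say whether they are individual eyes, study means or models, so the two widths may not be like for like.

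**Conclusion.** The concern holds in a limited form. The sample size is correct for its test. The error is in what is drawn from it: a detectable mean difference over 48 subjects is offered as evidence of image-level resolution, and it cannot be that. On the plan's own SD, single-eye 95% limits for the fitted radius are about ±2.35 mm, with about 40% of eyes more than 1 mm apart. A paired t-test of the mean alone cannot establish comparability in individual eyes.

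These figures assume zero bias, normal differences and a spread that is constant across eyes. The ±2.35 mm is not a maximum: about 5% of eyes would fall outside it. The pilot left a bias, whose size the text does not give, and a possible trend; a bias would shift the limits, and a trend would make one pair of limits inadequate. The 1.2 mm itself depends on halving the pilot SD.

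A reader might also take the sub-millimetre expectation in SA3. Justification & Feasibility as a ±1 mm agreement margin. It is not one: it is an anticipated curvature difference tied to MRI resolution, and the documents set no per-eye margin.

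**What to change.** 1. Reword the sentence after the Group 1 sample-size statement so that 0.5 mm is the mean bias detectable across 48 subjects. Remove the inference to resolution, or support it separately with a surface-level error and a stated abnormality size.
2. Make two results mandatory for Group 1: the mean OCT–MRI bias with its confidence interval, and the 95% limits of agreement with confidence intervals.
3. Prespecify and justify an acceptable per-eye difference in radius, and judge the limits against it. The sponsor should choose it, bearing in mind that the differences include MRI error, so wide limits would not by themselves show which method is at fault.
4. If the limits exceed that margin, restrict the conclusion in SA3. Expected Outcomes to group-mean agreement for research studies.

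The cost is protocol wording, one justified margin and one standard analysis of data already to be collected, with no added subjects or imaging. The drawback is that the claim becomes less favourable: at the planned SD, any margin tighter than about ±2.35 mm would be expected to fail.

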We will validate the algorithms by imaging a constructed model eye. The model consists of a custom-made +30 D rigid gas permeable contact lens (Essilor, center thickness 490 μm), a +20 D intraocular lens (SA60AT, Alcon), and a glass hemisphere with a 12.5 mm radius of curvature (64-496, Edmund Optics). These will be mounted into a lens tube at physiological distances and then immersed into balanced salt solution, leaving only the anterior surface of the contact lens ("cornea") exposed. The model eye will be imaged with the whole eye OCT and the surfaces recovered. After correction with the above algorithms, the curvature of the hemisphere will be compared to that of the manufacturer reference.

Clinical study. For the clinical studies, we will enroll two groups of subjects: 1. pseudophakic subjects with no known history of ocular pathology other than refractive error (no more than -6 D) and 2. pseudophakic and phakic subjects with high progressive myopia including those with staphylomas.

Group 1. The goal for the first group is to demonstrate in a normal eye the ability to accurately recreate the posterior eye with OCT spatially comparable to MRI (Fig. 10). We will only include monofocal pseudophakic individuals in this group. This reduces uncertainties by using a known manufactured lens. At the Duke Eye Center, the monofocal lens of choice is manufactured by Alcon, and the company has provided us with the optical prescriptions of their IOLs for research use under a non-disclosure agreement. With the optical properties of the IOL known, we anticipate being able to fully characterize these normal, pseudophakic eyes optically. This also provides a baseline from which phakic eyes can be studied.

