Group 2. After enrollment and data analysis of the first group, we will then examine the ability of OCT to provide spatially comparable images to MRI in eyes that are structurally abnormal. We will enroll 20 adult patients with progressive high myopia (more than -6 D) especially targeting those with posterior staphylomas – outpouchings of the posterior eye. These subjects can be pseudophakic or phakic. Phakic subjects will be required to be cyclopleged to ensure no dynamic lens changes during imaging. For phakic reconstructions, we will use age appropriate models of the natural lens indices as we have used in our previous study [52]. After recovery of the OCT and MRI surfaces, the OCT surface will be registered to the MRI surface at a common feature (e.g. optic nerve) and via cross-correlation. A root mean square deviation across the registered surfaces will then be calculated to quantify the topographic difference between the OCT and MRI surfaces.

SA3. Expected Outcomes. At the conclusion of this aim, we will have developed algorithms to spatially correct full eye OCT images and validated them with reference phantoms. We will also have tested the idea that spatially corrected OCT images will be comparable to MRI representations of the posterior eye first in pseudophakic normal eyes and then in pseudophakic and phakic myopic eyes. This will provide the basis for OCT to replace MRI for ophthalmic studies of ocular morphometry, lowering cost and logistical barriers to these types of studies while also providing higher resolution images over MRI. This has clinical utility for study of myopia progression and risk stratification based on prior studies associating deviations in ocular shape with pathologic myopia.

SA3. Potential Problems & Alternative Strategies. The FOV of our proposed posterior eye OCT channel will be 85° (or ~120° relative to center of the eye) – at least double that of standard retinal photography. This should be sufficient for measuring posterior eye shape as it encompasses the entire macula and reaches nearly to the equator of the eye. Should larger FOV be desired, though, we can use montaging as others have shown with OCT [54] to further increase our FOV. Because our whole eye OCT also concurrently images the anterior eye, our reconstructions can account for the relative change in position between the system and the eye to increase the accuracy of montaging and provide additional references for montage reassembly.

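### Group 2's only score, one RMS over the whole registered surface, is insensitive to a focal staphyloma, the main abnormality the group is meant to examine

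*Combined protocol and SAP*

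**What the plan says.** **Purpose.** SA3 Research Design, Group 2, sets out to "examine the ability of OCT to provide spatially comparable images to MRI in eyes that are structurally abnormal". SA3 Justification & Feasibility announces the same work: "we will compare surface topographies of myopic patients with known morphometric changes (e.g. staphylomas) imaged with MRI and OCT". The Figure 10 caption is narrower: "In a second study in subjects with staphylomas, we will use root mean square difference".

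**Entry.** The Group 2 paragraph reads: "We will enroll 20 adult patients with progressive high myopia (more than -6 D) especially targeting those with posterior staphylomas". The opening of the clinical study section describes the group as "pseudophakic and phakic subjects with high progressive myopia including those with staphylomas". Neither statement requires a staphyloma or sets a minimum number of eyes with one.

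**Score.** After the OCT surface is registered to the MRI surface, the plan states: "A root mean square deviation across the registered surfaces will then be calculated to quantify the topographic difference between the OCT and MRI surfaces". It specifies no regional error, signed error, maximum deviation or staphyloma depth, and no acceptable RMS. The 20 subjects come with no effect size, precision target or power.

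**The concern.** A staphyloma is a local departure from the general curve of the eye. A single RMS over the whole surface answers a different question: how far apart the two surfaces are on average. If OCT flattens the outpouching but follows the rest of the wall well, the average can be small.

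Flattening is a plausible failure here. SA3 Introduction says that uncorrected retinal OCT looks too flat, and the pilot left a bias against MRI after correction. Because RMS squares the deviations, it cannot tell systematic flattening from random scatter of the same size.

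No other specified analysis covers the point. Group 1 excludes ocular pathology other than refractive error, and its measure, radius of curvature, is also a whole-surface summary.

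At stake is the use the aim has in mind: OCT in place of MRI for posterior eye shape in myopia, including risk stratification from shape deviations. Those deviations carry the diagnostic information, and Group 2 is the only place where the plan examines them.

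**Working it through.** The plan gives no calculation for Group 2, so there is no figure to reproduce. The check asks how much of a local error survives in the whole-surface RMS.

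**Inputs from the documents**
- Scored field: about 120 degrees about the eye centre, so a cap of 60-degree half-angle (SA3 Potential Problems).
- Radius R: 12.5 mm (model eye, SA3 Research Design), with the range 10.8 to 14.1 mm (Figure 9 caption).

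**Assumptions, because the documents give no values**
- A circular abnormal region of width w = 6 to 10 mm.
- A uniform OCT error d inside it and e elsewhere.
- The whole OCT field is scored, with equal weight per unit area.

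**Formulas**
- Area share: f = [1 − cos(asin(w/2R))] / [1 − cos 60°]
- Whole-surface RMS = √(f·d² + (1 − f)·e²)

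At R = 12.5 mm the field is 2π × 12.5² × 0.5 = 491 mm².

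**Results for d = 1 mm, e = 0**

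| R (mm) | w (mm) | f | Whole-surface RMS (mm) | RMS inside region (mm) |
|---|---|---|---|---|
| 12.5 | 6 | 0.0292/0.5 = 5.8% | √0.058 = 0.24 | 1.0 |
| 12.5 | 10 | 0.0835/0.5 = 16.7% | √0.167 = 0.41 | 1.0 |
| 14.1 | 6 | 0.0229/0.5 = 4.6% | √0.046 = 0.21 | 1.0 |
| 10.8 | 10 | 0.1136/0.5 = 22.7% | √0.227 = 0.48 | 1.0 |

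The score keeps between a fifth and a half of the local error.

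**Sensitivity to the assumptions**
- Background error e = 0.25 mm, d = 1 mm, R = 12.5 mm: 0.34 mm (w = 6) to 0.47 mm (w = 10). At R = 10.8 mm and w = 10 mm: √(0.227 + 0.773 × 0.0625) = 0.52 mm.
- Deeper error, R = 12.5 mm, w = 6 to 10 mm, e = 0: d = 1.5 mm gives 0.36 to 0.61 mm; d = 2 mm gives 0.48 to 0.82 mm.
- Wider region, R = 12.5 mm, d = 1 mm, e = 0: w = 12.1 mm gives 0.50 mm; w = 15 mm gives √0.40 = 0.63 mm.
- Very large region: f = 30% with d = 2 mm gives √(0.30 × 4) = 1.10 mm.

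**Cross-check with a different shape.** A smooth, tapered outpouching 4 to 10 mm wide and 1 to 3 mm deep, wholly missed by OCT, was simulated on the 12.5 mm cap with no other error and a least-squares translation before scoring. The whole-surface RMS was 0.06 to 0.45 mm, against 0.35 to 1.20 mm inside the region and a peak error of 0.90 to 2.95 mm. The plan registers differently (a common feature plus cross-correlation), so this is supporting evidence only.

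**The case against.** The other side has several good points.

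- **No threshold.** A reader might infer that an RMS below 0.5 mm would count as agreement. The documents do not say so. The 0.5 mm figure is Group 1's detectable difference in radius of curvature, a different quantity in a different group. Group 2's RMS is there to quantify or describe. This stands: no criterion is being met wrongly.
- **Masking is not general.** The size of a staphyloma is assumed, and the Group 1 sample-size paragraph itself speaks of large-scale abnormalities. Wide or deep errors do raise the RMS, and RMS weights large errors more heavily than a mean absolute difference would. This stands, and it confines the point to focal or moderate errors.
- **The purpose is wider than staphylomas.** The Group 2 text speaks of abnormal structure, with staphylomas as the leading example; only the figure caption limits the study to them. A reader might infer that the 20 eyes could include almost no staphylomas. Nothing excludes that, but the stated targeting makes it an unsupported prediction.
- **Registration.** A reader might infer that aligning the surfaces first hides error. Any pointwise comparison needs a shared frame, including the regional one proposed here, so this is not a defect.
- **Images are stored.** Regional analysis could be added later without new scans. That is true, but a region chosen after the OCT surface has been seen is weaker evidence than one fixed beforehand.

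**Conclusion.** The point holds as a weakness in the choice of outcome. The one named score is a poor detector of the feature Group 2 mainly targets, and the entry text lets eyes with and without that feature be pooled. With a region 6 to 10 mm across, a 1 mm local error, no error elsewhere and R between 10.8 and 14.1 mm, the score is about 0.2 to 0.5 mm while the error inside the region is 1.0 mm. This rests on the assumed size and uniform error, and on equal-area scoring of the full field. A smaller scored area would dilute less.

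The documents do not support the stronger conclusion that Group 2 would pass a badly reconstructed staphyloma: there is no pass mark, and a large enough error would be visible. The disagreement between the Figure 10 caption and the entry text is one of wording, but it decides which population the result describes. Overall this is a worthwhile, low-cost improvement to a descriptive 20-subject study, not an error that invalidates it.

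**What to change.** - Keep the whole-surface RMS as planned.
- Pre-specify two further Group 2 results: RMS and mean signed OCT-minus-MRI deviation inside the abnormal region. Outline that region on MRI, by a written rule, without sight of the OCT surface.
- Report eyes with and without an MRI-confirmed staphyloma separately, giving the number of each.
- Base any statement about staphylomas on the regional result.
- Reconcile the Figure 10 caption with the entry text, so that it is clear whether Group 2 is a study of staphyloma or of high myopia enriched for it.

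The cost is one outline per MRI by existing study staff. It needs no extra subjects or scans. A fixed minimum number of staphyloma eyes is not proposed: the documents offer nothing from which to derive one, and it could slow recruitment.
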